# 10.3 Analysis Sets

For purposes of analysis, the populations and analysis data sets are defined in Table 10.3-1.

Table 10.3-1: Populations and Analysis Data Sets

| Population                                      | Description   |
|---|---|
| Enrolled  | All participants who sign informed consent.   |
| Randomized (FAS)                                | All participants who were randomized to any treatment arm in the study.   |
| Full Analysis Subgroup                          | All participants who were randomized to any treatment arm in the study and baseline s-PGA $\geq$ 3.   |
| Safety  | All randomized participants who take at least 1 dose of study intervention.  Participants will be analyzed according to intervention received.  |
| Defined Analysis Data Sets               | Description   |
| Analysis set for primary estimand of ss-PGA 0/1 | All randomized participants with baseline s-PGA $\geq$ 3; all available data up to Week 16 database lock. Participants who discontinued prior to Week 16 will be imputed as non-responders in the analysis dataset. Following the intent-to-treat principle, participants will be analyzed according to the intervention group assigned at randomization. |
|   | All randomized participants; all available data up to Week 16 database lock. Participants who discontinued prior to Week 16 will be imputed as non-responders in the analysis dataset. Following the intent-to-treat principle, participants will be analyzed according to the intervention group assigned at randomization.                              |

Table 10.3-1: Populations and Analysis Data Sets

| Population   | Description   |
|--|---|
| Analysis set for secondary estimand of PSSI 90                 | All randomized participants with baseline s-PGA ≥ 3; all available data up to Week 16 database lock. Participants who discontinued prior to Week 16 will be imputed as non-responders in the analysis dataset. Following the intent-to-treat principle, participants will be analyzed according to the intervention group assigned at randomization.              |
|  | All randomized participants; all available data up to Week 16 database lock. Participants who discontinued prior to Week 16 will be imputed as non-responders in the analysis dataset. Following the intent-to-treat principle, participants will be analyzed according to the intervention group assigned at randomization.                                      |
| Analysis set for secondary estimand of Scalp-specific itch NRS | All randomized participants with baseline s-PGA $\geq$ 3; all available data up to Week 16 database lock. Participants who discontinued prior to Week 16 will be imputed using multiple imputation in the analysis dataset. Following the intent-to-treat principle, participants will be analyzed according to the intervention group assigned at randomization. |
|  | All randomized participants; all available data up to Week 16 database lock. Participants who discontinued prior to Week 16 will be imputed using multiple imputation in the analysis dataset. Following the intent-to-treat principle, participants will be analyzed according to the intervention group assigned at randomization.                              |
| Analysis set for secondary estimand of s-PGA 0/1               | All randomized participants with baseline s-PGA $\geq$ 3; all available data up to Week 16 database lock. Participants who discontinued prior to Week 16 will be imputed as non-responders in the analysis dataset. Following the intent-to-treat principle, participants will be analyzed according to the intervention group assigned at randomization.         |
| Analysis set for safety  | All safety events reported for all randomized participants who are exposed to study intervention. For participants who discontinue study intervention all post-discontinuation up to day 28 post last dose of study intervention will be included in the safety summaries. Participants will be analyzed according to intervention received.                      |

NRS, numerical rating scale; PSSI, Psoriasis Scalp Severity Index; s-PGA, static Physician Global Assessment; ss-PGA, scalp-specific Physician Global Assessment.

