**Laboratory Tests** 

**Table 2-1:** Screening Procedural Outline (IM011220)

| Procedure                            | Screening Visit
(Day –28 to Day –1) | Notes   |
|--------------------------------------|--|---|
|                                      |  |   |
| TSH                                  | X                                      | Abnormal TSH will be exclusionary. If TSH above normal reference range, test free T4; if TSH below normal range, test free T4 and T3 (see Section 6.2).   |
| Pregnancy test (serum)               | X                                      | For WOCBP only; see APPENDIX 4 Serum (minimum sensitivity equivalent units 25 IU/L or equivalent units of hCG) to be done at Screening Visit.  The participant must be excluded from participation if the serum pregnancy result is positive.   |
| FSH                                  | X                                      | If needed to document post-menopausal status, as defined in Section 9.4.  Females under the age of 55 years must have a serum FSH level > 40 mIU/mL to confirm menopause.   |
| AE Reporting                         |                                 |   |
| Monitor for SAEs                     | X                                      | All SAEs must be collected from the date of participant's written consent until 30 days post discontinuation of dosing or participant's participation in the study if the last scheduled visit occurs at a later time. All AE (SAEs or nonserious AE) related to SARS-CoV-2 infection collected from time of consent. |
| Clinical Efficacy Assessments |  |   |
| ss-PGA                               | X                                      |   |
| SSA                                  | X                                      |   |
| PSSI                                 | X                                      |   |
| BSA                                  | X                                      |   |

AE, adverse event; ALT, alanine aminotransferase; AST, aspartate aminotransferase; BMI, body mass index; BSA, body surface area; ECG, electrocardiogram; FSH, follicle-stimulating hormone; ; hCG, human

\* - WHO global lists of high burden countries for TB, TB/HIV, and MDR/RR-TB, 2021–2025; APPENDIX 5.

Table 2-2: On-Intervention Procedural Outline (IM011220), Day 1 through Week 20

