| Study Intervention             |                                      |                                       |                                       |                                       |   |   |       |
| Dispense Study
Intervention | X                                    | X                                     | X                                     | X                                     |   |   |       |

Table 2-3: On-Intervention Procedural Outline, (IM011220) Week 24 through Week 52

| Procedures                       | Week 24
D169
(±3 d)
Visit 9 | Week 28
D197
(±3 d)
Visit 10 | Week 32
D225
(±3 d)
Visit 11 | Week 40
D281
(±3 d)
Visit 12 | Week 52
(EOT or
ET a )
D365
(±3 d)
Visit 13 | Safety Follow-up (Week 56 or Post-Treatment Follow up a ) D393 (±3 d) Visit 14 | Notes |
|----------------------------------|--------------------------------------|---------------------------------------|---------------------------------------|---------------------------------------|---|---|-------|
| Study Intervention
Compliance | X                                    | X                                     | X                                     | X                                     | X   |   |       |

AE, adverse event; BSA, body surface area; d, days; D, Day;

EOT, End of Treatment; ET, early termination;

IP, investigational product; IRT, interactive response technology;

PASI, Psoriasis Area and Severity Index; PE, physical examination; PRO, patient-reported outcome;

PSSI, Psoriasis Scalp Severity Index; SAE, serious adverse event; Scalpdex, Scalp dermatitis-specific quality of life instrument; s-PGA, static Physician Global Assessment; ss-PGA, scalp-specific Physician Global Assessment; WOCBP, women of childbearing potential.

Note: When multiple assessments are conducted at a single visit, the following is the order in which they should be done as applicable:

- 1)
- 2) Safety assessments (eg, vitals, AEs)
- 3) Clinical efficacy assessments
- 4) Laboratory tests (eg, safety laboratory tests). The dose of the IP on a visit day is to be taken after blood draws for laboratory tests.

<sup>a EOT/ET visit for participants who discontinue treatment any time prior to completing Week 52 of active treatment period. Safety follow-up visit occurs 28 days ± 3 days after the last dose of study treatment.

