  - Exception: The shampoos that contain corticosteroids may be initiated at Week 20 and at any of the subsequent study visits per Investigator's discretion in participants who have ss-PGA scores  $\geq 3$  (Section 7.7).
- Live attenuated vaccines (including, but not limited to, any live attenuated COVID-19 vaccines) should not be used during the study, including the safety follow-up period of 60 days following last dose of IP (see Section 7.7.4 for permitted vaccines).

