## 9.2.2 Time Period and Frequency for Collecting AE and SAE Information

The collection of nonserious AE information should begin at initiation of study intervention until discharge from the study (ie, final study visit for a given participant), at the timepoints specified in the Schedule of Activities (Section 2).

Appendix 1 of the  $\rm IB^{26}$  represents the Reference Safety Information to determine expectedness of SAEs for expedited reporting.

All SAEs must be collected from the time of signing the consent, including those thought to be associated with protocol-specified procedures, and within 30 days following discontinuation of dosing.

The Investigator must report any SAE that occurs after these time periods and that is believed to be related to study intervention or protocol-specified procedure.

- Medical occurrences that begin before the start of study intervention but after obtaining informed consent will be recorded on the appropriate section of the eCRF module.
- All SAEs will be recorded and reported to Sponsor or designee within 24 hours, as indicated in APPENDIX 3.
- The Investigator will submit any updated SAE data to the Sponsor or designee within 24 hours of updated information being available.

Investigators are not obligated to actively seek AEs or SAEs in former study participants. However, if the Investigator learns of any SAE, including a death, at any time after a participant has been discharged from the study, and he/she considers the event reasonably related to the study intervention or study participation, the Investigator must promptly notify the Sponsor.

The method of evaluating and assessing causality of AEs and SAEs and the procedures for completing and reporting/transmitting SAE reports are provided in APPENDIX 3.

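### For participants who stop treatment early, the safety summaries end at day 28 after last dose, short of the plan's own SAE collection window (day 30) and latest follow-up visit (day 31)

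*Combined protocol and SAP*

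**What the plan says.** The safety row of Table 10.3-1 (Section 10.3) contains two rules. The first is general and has no day limit: "All safety events reported for all randomized participants who are exposed to study intervention". The second is narrower and applies to participants who discontinue study intervention: their post-discontinuation data "up to day 28 post last dose of study intervention will be included in the safety summaries". Day 28 is the only numerical post-dose limit that the document gives for any safety analysis. Section 10.4.5.1 refers to treatment-emergent AEs without defining a window.

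The collection rules run longer:

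- **SAEs, Section 9.2.2:** from consent and "within 30 days following discontinuation of dosing".
- **SAEs, Table 2-1:** "until 30 days post discontinuation of dosing or participant's participation in the study if the last scheduled visit occurs at a later time".
- **Nonserious AEs, Section 9.2.2:** from the start of study intervention to the participant's final study visit.
- **Follow-up visit, Table 2-3 footnote a:** "Safety follow-up visit occurs 28 days ± 3 days after the last dose of study treatment".
- **After stopping treatment, Section 8.1.2:** participants stay in follow-up for outcome data until the study concludes.

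Section 10.4.5 says that safety is analysed through Week 16 and then to end of study. Sections 10.4.5.2 and 10.4.5.3 summarise vital-sign and laboratory abnormalities at each scheduled visit.

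**The concern.** An analysis window may be shorter than a collection window, but the plan should then say so and give a reason. Here no reason is given, and other sentences in the plan point the other way. For an early discontinuer, an SAE that starts on day 29 must be collected and reported to the sponsor. The general sentence in Table 10.3-1 and Section 10.4.5 would count it, while the day-28 sentence would not. A programmer cannot follow all three.

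The people affected matter for safety, because Section 8.1 makes AEs and laboratory abnormalities grounds for stopping treatment. What is at stake is which late events in these participants appear in the summary tables. Efficacy results are not involved.

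**Working it through.** This is day arithmetic. No power or alpha figure enters.

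**1. Reproduce the plan's visit timing.** Table 2-3 puts Week 52 at D365 and Week 56 at D393.

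- 393 − 365 = 28 days, which agrees with footnote a.
- 28 ± 3 gives a permitted visit on days 25 to 31 after last dose.

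**2. Compare each collection end with the day-28 limit, for early discontinuers.**

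| Item | Collected to | Days beyond day 28 |
|---|---|---|
| SAEs, Section 9.2.2 | day 30 | 30 − 28 = 2 |
| SAEs, Table 2-1, if the last visit is on day 31 | day 31 | 31 − 28 = 3 |
| Nonserious AEs, if the final visit is the follow-up visit | up to day 31 | 31 − 28 = 3 at most |

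**3. Longer follow-up.** Assume that Section 8.1.2 keeps a discontinuer in follow-up to D393 and that safety data are part of that follow-up. The time outside the window is then 393 − (day of last dose) − 28.

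- Stop at Week 8 (D57): 393 − 57 − 28 = 308 days.
- Stop at Week 16 (D113): 393 − 113 − 28 = 252 days.
- Stop at Week 40 (D281): 393 − 281 − 28 = 84 days.

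If follow-up instead ends at the 28-day visit, as Section 5.1.5 can be read, the gap is at most the 3 days in step 2.

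**4. Reach into the placebo comparison.** The safety objective in Table 4-1 covers Week 0 to Week 16 (D113). The first excluded day is day 29 after last dose. It falls on or before D113 only if the last dose was on or before D113 − 29 = D84, about Week 12 (D85).

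**5. What the cut-off does not remove.** An AE recorded at a day-31 visit that began by day 28 is still inside the window if events are placed by onset date. The plan does not state the placement rule, so onset date is my assumption. Laboratory and vital-sign results at the follow-up visit are summarised by scheduled visit under Sections 10.4.5.2 and 10.4.5.3, so they are not clearly excluded.

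**The case against.** The strongest reply is that a post-dose window is ordinary practice. Day 28 matches the nominal follow-up visit and lies far beyond the roughly 3 days that Section 9.3 gives for five half-lives, so events on days 29-31 say little about the drug. The data are still collected, SAEs are still reported, and Section 10.4 leaves data-handling detail to a SAP whose separate text is not in the document. Most of this stands. A 28-day window would be defensible if the plan stated it as a choice. It does not, and a later SAP would still have to choose between protocol sentences that disagree.

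A reader might infer more than the documents support, in three ways:

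- **That the cut-off applies to all of the roughly 150 participants.** The limiting sentence covers those who discontinue study intervention, and Section 5.1.5 and Table 2-3 footnote a use that idea for stopping before Week 52. For completers the row's first sentence sets no limit.
- **That 2 of 30 SAE days (7%) or 3 of 7 permitted visit days (43%) measure the loss.** These are shares of calendar days. The document gives no event rates and no distribution of visit days, so neither figure estimates lost events.
- **That everything found at a visit on days 29-31 is discarded.** Step 5 of the working shows why this does not follow.

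Section 7.7.1 describes the post-treatment period as "including the safety follow-up period of 60 days following last dose of IP". That wording belongs to a live-vaccine restriction and sets no AE collection or analysis window. It disagrees with the 28-day follow-up in Section 5.1.5 and needs reconciling, but it does not bear on this point.

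**Conclusion.** The point holds for participants who discontinue study intervention early. Read literally, Table 10.3-1 leaves out of the safety summaries SAEs that start on days 29-30 and nonserious AEs that start after day 28, although the plan requires both to be collected. It also conflicts with the first sentence of its own row and with Section 10.4.5.

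The mismatch is 2 to 3 days around the follow-up visit. It could reach 308 days for a Week 8 stop, but only if Section 8.1.2 is read as continuing safety collection to D393. The expected number of events is small and cannot be estimated from the document. The Week 0-16 safety comparison is affected only for those who stop by about Week 12. The conclusion rests on placing events by onset date and on reading discontinuation as stopping before Week 52. This is a modest but clear correction that belongs in the plan before the Week 16 database lock.

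**What to change.** In the safety row of Table 10.3-1, replace the day-28 limit with 30 days after last dose or the safety follow-up visit, whichever is later. This closely follows the SAE rule in Table 2-1 and covers the visit window to day 31. Add that events after that point, in discontinuers still followed under Section 8.1.2, will be listed, and align Section 10.4.5 so that the two places agree. State that AEs are assigned to the window by onset date.

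The cost is a sentence or two and one programming cut-off, with no new data. The summaries will contain slightly more off-drug time for early discontinuers. Separately, the sponsor should reconcile the 60-day wording in Section 7.7.1 with the follow-up period stated elsewhere.

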# 10.4 Statistical Analyses

The statistical analysis plan (SAP) will be developed and finalized before the primary analysis database lock and will describe the selection of participants to be included in the analyses, and procedures for accounting for missing, unused, and spurious data. Below is a summary of planned statistical analyses of the primary and secondary endpoints. A description of the participant population will be included in the clinical study report, including subgroups of age, gender, race, and other study specific populations and demographic characteristics. A description of participant disposition will also be included in the clinical study report.

#### 10.4.1 General Considerations

Categorical data will be summarized as frequency counts and percentages. Continuous data will be summarized using n, mean, standard deviation, median, minimum, and maximum unless otherwise specified. Efficacy values will be summarized for all visits in which the variable is assessed. Baseline values are defined as the last non-missing value prior to the first dose of study drug unless otherwise indicated.

During the first 16 weeks of treatment, data will be presented for the following interventions:

- Deucravacitinib 6 mg QD
- Placebo

After Week 16, data will be presented for the following interventions:

- Deucravacitinib 6 mg QD
- Placebo Deucravacitinib 6 mg QD (starting at Week 20 through Week 52)

The primary endpoint, ss-PGA 0/1 response, is defined as a proportion of participants with an ss-PGA score of 0 (clear) or 1 (almost clear) with at least a 2-point reduction from baseline at Week 16. The key secondary endpoints assessed at Week 16 are PSSI 90 response, change from baseline in scalp-specific itch NRS score, and s-PGA 0/1 response (sub-population only). PSSI 90 is defined as a proportion of participants who achieve at least a 90% improvement from baseline in the PSSI score, and s-PGA 0/1 is defined as a proportion of participants with a s-PGA score of 0 (clear) or 1 (almost clear) with at least a 2-point reduction from baseline at Week 16.

**Table 10.4.1-1:** Definition of Estimands for Primary and Key Secondary Endpoints

| Primary Endpoint      |  |  |  |  |
|-----------------------|--|--|--|--|
| Estimand
Attribute | Definition   |  |  |  |
| Treatment             | Deucravacitinib 6 mg QD vers   | Deucravacitinib 6 mg QD versus placebo |  |  |
| Population            | FAS population and FAS sub-population                                      |  |  |  |
| Variable              | ss-PGA 0/1   | ss-PGA 0/1                             |  |  |
| ICEs                  | Event  | Strategy                               | Description                                    |  |
|                       | Discontinuation of intervention or study early prior to Week 16 assessment | Composite variable                     | Participant will be counted as a non-responder |  |

Table 10.4.1-1: Definition of Estimands for Primary and Key Secondary Endpoints

|                                 | Lost to follow-up prior to
Week 16 or otherwise
missing endpoint data at
Week 16 assessment | Composite variable | Participant will be counted as a non-responder   |
|---------------------------------|--|--------------------|--|
|                                 | Start a protocol prohibited medication/therapy   | Treatment policy   | Participants will be included in the primary analysis regardless of the occurrence of the ICE according to the respective endpoint definition. |
|                                 | Missing assessment at
Week 16 due to SARS-CoV-2   | While on treatment | Participants will be excluded from the primary analysis if the Week 16 assessment was not completed due to SARS-CoV-2                          |
| Population-
level
Summary | Odds ratio of achieving ss-PGA   | A 0/1              |  |
| Key Secondary            | Endpoints  |                    |  |
| Estimand
Attribute           | Definition   |                    |  |
| Treatment                       | Deucravacitinib 6 mg QD versus placebo   |                    |  |
| Population                      | FAS population and FAS sub-population  |                    |  |
| Variable                        | PSSI 90  |                    |  |
| ICEs                            | Event  | Strategy           | Description  |
|                                 | Discontinuation of intervention or study early prior to Week 16 assessment                           | Composite variable | Participant will be counted as a non-responder   |
|                                 | Lost to follow-up prior to
Week 16 or otherwise
missing endpoint data at
Week 16 assessment | Composite variable | Participant will be counted as a non-responder   |
|                                 | Start a protocol prohibited medication/therapy   | Treatment policy   | Participants will be included in the analysis regardless of the occurrence of the ICE according to the respective endpoint definition.         |
|                                 | Missing assessment at Week
16 due to SARS-CoV-2   | While on treatment | Participants will be excluded from the analysis if the Week 16 assessment was not completed due to SARS-CoV-2                                  |
| Population-
level
Summary | Odds ratio of achieving PSSI 9   | 0                  |  |

Table 10.4.1-1: Definition of Estimands for Primary and Key Secondary Endpoints

| Estimand
Attribute           | Definition   |                              |  |
|---------------------------------|--|------------------------------|--|
| Treatment                       | Deucravacitinib 6 mg QD versus placebo   |                              |  |
| Population                      | FAS population and FAS sub-  | population                   |  |
| Variable                        | Change from baseline in Scalp  | -specific itch Numeric Ratin | ng Scale (NRS)   |
| ICEs                            | Event  | Strategy                     | Description  |
|                                 | Discontinuation of intervention or study early prior to Week 16 assessment                           | Composite variable           | Missing data will be imputed using multiple imputation   |
|                                 | Lost to follow-up prior to
Week 16 or otherwise
missing endpoint data at
Week 16 assessment | Composite variable           | Missing data will be imputed using multiple imputation   |
|                                 | Start a protocol prohibited medication/therapy   | Treatment policy             | Participants will be included in the analysis regardless of the occurrence of the ICE according to the respective endpoint definition. |
|                                 | Missing assessment at Week
16 due to SARS-CoV-2   | While on treatment           | Participants will be excluded
from the analysis if the
Week 16 assessment was not
completed due to SARS-
CoV-2             |
| Population-
level
Summary | Adjusted mean difference betw  | veen deucravacitinib 6 mg Q  | D and placebo  |
| Estimand
Attribute           | Definition   |                              |  |
| Treatment                       | Deucravacitinib 6 mg QD vers   | us placebo                   |  |
| Population                      | FAS sub-population   |                              |  |
| Variable                        | s-PGA 0/1  |                              |  |
| ICEs                            | Event  | Strategy                     | Description  |
|                                 | Discontinuation of intervention or study early prior to Week 16 assessment                           | Composite variable           | Participant will be counted as a non-responder   |
|                                 | Lost to follow-up prior to
Week 16 or otherwise
missing endpoint data at
Week 16 assessment | Composite variable           | Participant will be counted as a non-responder   |
|                                 | Start a protocol prohibited medication/therapy   | Treatment policy             | Participants will be included
in the primary analysis
regardless of the occurrence
of the ICE according to the                |

Table 10.4.1-1: Definition of Estimands for Primary and Key Secondary Endpoints

|                                 |  |                    | respective endpoint definition.   |
|---------------------------------|--|--------------------|---|
|                                 | Missing assessment at Week
16 due to SARS-CoV-2 | While on treatment | Participants will be excluded
from the primary analysis if
the Week 16 assessment was
not completed due to
SARS-CoV-2 |
| Population-
level
Summary | Odds ratio of achieving s-PGA                      | 0/1                |   |

FAS, Full Analysis Set; ICE, intercurrent event; NRS, numerical rating scale; PSSI, Psoriasis Scalp Severity Index; QD, once daily; SARS-CoV-2, severe acute respiratory syndrome coronavirus 2; ss-PGA, scalp-specific Physician Global Assessment; s-PGA, static Physician Global Assessment.

